Statistical Analysis Plan

A Prospective Study of Human Bone Adaptation Using a Novel in Vivo Loading Model

ID: 13-111

NCT #: not yet assigned

Originally created: 1/12/2012

Last updated: 1/12/2012 by [name]

Statistical Analysis Plan

Originally created: 1/12/2012

Last updated: 1/12/2012 by [name]

Statistics and Expected Outcomes:

An intent to treat analysis will not be employed here because the purpose of this research is to determine the link between *actual strains applied to bone* and the bone adaptive response. The present study is not intended to address the degree to which mechanical loading is an effective means to improve bone strength in a public health setting. Accordingly, adherence to the mechanical loading protocol is expected to influence the degree of adaptation and will be considered a potential explanatory variable for the following analyses.

For Experiment 1, hypotheses are related to the effect of strain magnitude.

For Experiment 2, hypotheses are related to the effect of strain rate. In both cases, the statistical analysis plan is the same, but tests will be performed on the corresponding variables (strain magnitude, or strain rate).

Hypothesis 1a: Bone mass will increase proportionally to the applied strain.

This hypothesis will be tested in two ways. In the first analysis, subjects will be analyzed by group (control, low, and high strain magnitude groups). For the group analysis, the 12-month change in whole radius total BMC will be analyzed as the primary dependent variable in a linear regression model with coefficients representing contrasts between each of the two experimental groups and the control group. Secondary outcome measures of trabecular BMC, ultra-distal BMC, fracture strength, moments of inertia, and others, will also be compared between groups using regression models for change scores at each of the four time points.

If our hypothesis is supported then there will be little change in the control group, a small but significantly higher increase in the 1800 $\mu\epsilon$ group, and a large and significantly higher increase in the 3600 $\mu\epsilon$ group. Similar models will be fit predicting change from baseline to 3, 6, and 9 months.

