In the second analysis, we will consider the *actual* strain magnitudes achieved by each subject, (which may differ from the group assigned strain), as a continuous variable, and will set the strain magnitude for control subjects to zero. The underlying assumption in doing this is that the baseline daily activity for *all* subjects is approximately equal, and is sufficient to maintain bone homeostasis. For this analysis, all four time points will be combined into a single model to examine changes across time after the loading regime has ended, and to compare the levels of applied strain. The dependent variable is the change score (in whole radius total BMC) from baseline; the independent variables are level of strain, time (3, 6, 9, 12 months), and a random intercept term for each subject to handle collinearity within repeated measurements. As in the first analysis method, secondary outcome measures of regional BMC, fracture strength, and others, will be considered as well.

If our hypothesis is supported then strain magnitude will be a significant predictor of change in whole radius total BMC and other related variables.

Hypothesis 1b: High initial bone mass, physical activity levels, and grip strength will be associated with diminished adaptive response for a given strain magnitude.

To test this hypothesis, initial BMC, grip strength, and physical activity will be added as potential covariates for the statistical models described in Hypothesis 1a.

If our hypothesis is supported then we would expect to observe an inverse relationship (negative coefficient) between initial bone mass, physical activity, grip strength, and change in BMC per group or per unit applied strain.

Hypothesis 1c: Bone structural changes will include increases in cortical diameter and thickness, and increased trabecular bone mass near the endosteal surface.

To test this hypothesis, the following variables will be examined:

For cortical diameter and thickness: integral and cortical bone mass and bone volume, compressive and bending strength index, and cross-sectional moments of inertia (bending and torsional)

For trabecular bone: trabecular bone mass and volume, cross sectional trabecular moments of inertia

Using the methods described for testing hypothesis 1a, changes in each of the specific variables listed will be examined at each time point. Here, the primary interest is in which specific quantities show the largest strain-related change.

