If our hypothesis is supported, we would expect to observe significant strain-dependant increases in each of the variables listed for the experimental groups, but not in the control group.

Hypothesis 1d: Local regions experiencing high strain magnitudes will experience greater local increases in BMC than regions experiencing low strain magnitudes.

This hypothesis will be tested using only subjects in the experimental conditions. For each subject, all of the elements within the baseline FE model will be divided into quartiles based on actual Von Mises equivalent strain occurring within each element. Of interest for the present analysis are elements in the highest strain quartile and the lowest strain quartile. (Note that Von Mises equivalent strains always have a positive sign.) For each of these quartile groups the change in QCT voxel density for those voxels corresponding to the location of the elements will be determined. We will use a Student's t-test to compare the average voxel density change in high strain versus low strain quartiles.

If our hypothesis is supported then elements experiencing the highest Von Mises strain will have significantly greater increases in density compared to elements experiencing the lowest Von Mises strain. Our underlying assumption in using the highest and lowest quartiles is that a minimum strain threshold is required to initiate an increase in density. Therefore, including all elements in the analysis, most of which do not exceed this threshold, may make it difficult to detect a local effect, if one is present.

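### Hypothesis 1b asks who responds less to loading, but its planned test reads an additive covariate coefficient averaged over loaded women and unloaded controls

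*SAP*

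**What the plan says.** SAP, Hypothesis 1b, states that high initial bone mass, physical activity and grip strength "will be associated with diminished adaptive response for a given strain magnitude". The whole method is one sentence: "initial BMC, grip strength, and physical activity will be added as potential covariates for the statistical models described in Hypothesis 1a". Support is a negative coefficient relating these variables to "change in BMC per group or per unit applied strain".

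Hypothesis 1a supplies two models, and both contain the controls:

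- The group model is a linear regression with "coefficients representing contrasts between each of the two experimental groups and the control group".
- The continuous model has strain, time and a random subject intercept, and "will set the strain magnitude for control subjects to zero".

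Neither model has a covariate × group or covariate × strain term, and Hypothesis 1b adds none. Nor does it leave the controls out. Hypothesis 1d does so explicitly: "This hypothesis will be tested using only subjects in the experimental conditions". The opening section of the SAP applies the same plan to Experiment 2, with strain rate in place of strain magnitude.

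**The concern.** An adaptive response is a response to loading. The claim that it is smaller in some women is a claim that the effect of group or strain depends on the covariate. The criterion's own wording, change per unit of applied strain, describes a strain slope that varies with the covariate. A covariate entered additively does not estimate that. It estimates how change in BMC varies with the covariate in all women, including those who apply no load.

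A slope shared by unloaded controls would therefore be reported as weaker adaptation to loading. Conversely, real modification is averaged with the control slope and can be diluted or hidden. What is at stake is a wrong conclusion about who responds to loading. The primary result is not at stake.

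**Working it through.** The documents give no alpha, SD, precision or effect size for 1b, so there is no planned figure to reproduce.

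**Inputs from the documents.** Protocol, Group Assignment: 20 low, 20 high and 20 control women per comparison. Aim 1 strain targets are 1800 and 3600 µε, which with control at zero gives relative strain 0, 0.5, 1. Aim 2 rate targets are 4500 and 36,000 µε/s; 4500/36,000 = 0.125, which gives 0, 0.125, 1.

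**Assumptions.** Residual SD 1, standardised covariates unrelated to group, strains at target, and a one-sided 2.5% test for a negative coefficient. Slopes are in residual SDs per covariate SD.

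**Step 1: what the coefficient estimates.** With equal groups it is the mean of the within-group slopes:

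pooled coefficient = (b_control + b_low + b_high)/3 = control slope + modification in the high group × mean share.

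The mean share depends on the shape of the modification:

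- Linear in strain, Aim 1: (0 + 0.5 + 1)/3 = 0.50
- Linear in strain rate, Aim 2: (0 + 0.125 + 1)/3 = 0.375
- Slow group has half: 0.50
- Both loaded groups equal: (0 + 1 + 1)/3 = 0.67
- High group only: 1/3 = 0.33

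With no modification the coefficient equals the control slope.

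**Step 2: a plausible control slope for initial BMC.** Error e in the baseline value enters the covariate positively and the change score negatively, so

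correlation = −e² / (SD of observed baseline × SD of observed change).

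The assumed ranges are e 1–2%, between-woman SD 12–15% and true-change SD 1–2%.

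- Smallest: −1/(√(15² + 1) × √(2² + 2)) = −1/(15.03 × 2.45) = −0.027
- Middle (1.5%, 13.5%, 1.5%): −2.25/(13.58 × 2.60) = −0.064
- Largest: −4/(√(12² + 4) × √(1 + 8)) = −4/(12.17 × 3) = −0.110

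**Step 3: false support with no modification.** The SE of the pooled coefficient is about 1/√60 = 0.13. A slope of −0.11 then gives Φ(−1.96 + 0.85) ≈ 13%. Simulation (20,000 runs) agrees:

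| Common slope | Additive, Aim 1 | Additive, Aim 2 | Interaction, either Aim |
|---|---|---|---|
| −0.03 | 4.0–4.1% | 3.9–4.0% | 2.3–2.7% |
| −0.11 | 12.6% | 13.0–13.1% | 2.4–2.5% |

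The middle slope of −0.064 gives about 7%. With three covariates entered jointly (Aim 1, slope −0.11, correlations between covariates 0 to 0.5), the additive test gives about 10–12% and the interaction 2–3%.

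**Step 4: power when modification is real.** The high-group modification is −0.5 and the control slope is zero.

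| Aim and shape | Additive (continuous) | Covariate × strain or rate | Covariate × group (high) |
|---|---|---|---|
| 1, linear | 45.7% | 32.1% | 31.4% |
| 1, loaded groups equal | 67.0% | 31.9% | 31.5% |
| 1, high group only | 23.3% | 32.0% | 31.5% |
| 2, linear | 27.8% | 36.8% | 31.4% |
| 2, slow group half | 44.5% | 27.3% | 31.4% |
| 2, loaded groups equal | 67.3% | 17.1% | 31.3% |

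If the slopes were +0.5, 0 and −0.5 (Aim 1), the additive test would detect 3% and the interaction 83%.

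**Step 5: the continuous interaction in Aim 2.** It is unbiased only if modification is linear in rate. For equal shares (0, 1, 1) the regression on (0, 0.125, 1) has covariance 1.125/3 − 0.375 × 0.667 = 0.125 and variance 0.198, so −0.5 is estimated as −0.5 × 0.63 = −0.32. If the slow group has half, the estimate is −0.42. The group-coded term recovers −0.50 in each case.

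**The case against.** **The wording can be read more kindly.** Holding strain fixed is what an additive covariate does, and the phrase about change per unit of strain suggests that the authors had interactions in mind. The first reading still counts a slope seen in unloaded women as reduced response to loading. If the second is right, the term has to be written down, because no model in the SAP contains it.

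**The control slope may be near zero.** The Protocol (Rationale for this population) says that bone measures hold at peak to age 40. The SAP assumes that baseline daily activity "is approximately equal, and is sufficient to maintain bone homeostasis" and expects that "there will be little change in the control group". This makes a large control slope less likely. But a small mean change does not fix the slope on a covariate at zero, and measurement error alone makes it negative for initial BMC. No such mechanism is claimed for grip strength or activity, so the false-support figures are argued only for initial BMC.

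**The figures rest on assumed inputs.** This stands. The 13% needs every input at its least favourable value, and the middle of the range gives about 7%.

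**The simulation uses one change score, not the repeated-measures model.** With balanced data and subject-level covariates, that model reduces to subject means over the four visits. If true change is the same at each visit, the largest slope becomes −4/(12.17 × √(1 + 4 + 1)) = −0.13, slightly worse. Achieved strain may also correlate with initial BMC or grip strength, which the identity in Step 1 ignores.

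**Interactions cost power.** This also stands. If the control slope really is zero, the pooled coefficient is often the more powerful test (Step 4). That advantage depends on a condition which the additive model cannot check.

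**Conclusion.** The concern holds. As written, the test of 1b does not match the hypothesis: it estimates an average covariate slope that includes unloaded women. This follows from the model terms and needs no assumed figure.

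The size of the harm is illustrative. For initial BMC, false support is about 4–13% where 2.5% is nominal, given the assumed precision and SDs. A true modification shows at one third to two thirds of its high-group size, depending on its shape, if the control slope is zero. Hypothesis 1b is not the primary analysis, so the SAP should be corrected, but the main result is not in doubt.

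**What to change.** For both experiments, mean-centre each covariate, keep its main effect as adjustment only, and add:

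- covariate × group terms to the group model;
- covariate × strain (Experiment 1) or covariate × strain rate (Experiment 2) to the continuous model.

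Base the 1b conclusion on the interaction estimates with confidence intervals, and report the covariate slope in controls beside them. In Experiment 2 give weight to the group-coded interaction: the slow group also loads to the target force, so modification need not be linear in rate (Step 5). State as well whether change in BMC is absolute or percent, because the SAP does not say and an interaction with initial BMC can depend on it.

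The cost is SAP wording and product terms: three in the continuous model and six in the group model if all covariates enter together. The group model then has 1 + 2 + 3 + 6 = 12 coefficients for 60 women. No new data are needed.

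The drawback is imprecision. The interaction SE is 0.31–0.34 SD per covariate SD with one covariate at a time, and in Aim 1 0.35–0.44 with three jointly. A non-significant interaction will say little, so the intervals should carry the conclusion.

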i. Radiation Dose: Each DXA scan exposes subjects to a total radiation dose of 0.05 mrem and subjects will receive one DXA scan each during screening. CT scans will result in an estimated radiation dose to subjects of 9 mrem per scan. HR-pQCT scans result in an effective radiation dose of 0.3 mrem per scan.

Subjects will receive 20.45 mrem (1 DXA plus 1 CT scan per arm x 2 arm x 9 mrem/scan plus 4 HR-pQCT scans/arm x 0.3 mrem/scan) over the first 12 month period, and 19.8 mrem (1 CT scan per arm x 2 arms + 3 HR-pQCT scans/arm x 2 arms) over the second 12 month period is expected.

ii. Mechanical Loading: Direct loading to the distal radius may cause some discomfort to subjects.

The alternative is to not participate in the research study.

2. Adequacy of Protection Against Risks

a. Recruitment and Informed Consent

Subjects will be recruited through physician referrals and by use of flyers, brochures, and word of mouth. Subjects will contact the Biomechanics Laboratory in response to either being directly asked to participate, or to seeing information about the study. If a subject appears to meet the study criteria, a letter of invitation will be sent to the potential subject and an appointment will be scheduled for them to speak with a member of the investigative team.

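### Hypothesis 1b: if initial BMC is the scan subtracted to form the change, its main-effect coefficient is not centred on zero, so a negative sign alone is weak evidence

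*SAP*

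**What the plan says.** Under Hypothesis 1a of the SAP, the group model is specified so that "the 12-month change in whole radius total BMC will be analyzed as the primary dependent variable in a linear regression model". In the second, repeated-measures analysis, "The dependent variable is the change score (in whole radius total BMC) from baseline", at 3, 6, 9 and 12 months, with "a random intercept term for each subject to handle collinearity within repeated measurements". One baseline value is therefore subtracted at all four visits.

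Hypothesis 1b states that high initial bone mass, physical activity and grip strength "will be associated with diminished adaptive response for a given strain magnitude". The test is that "initial BMC, grip strength, and physical activity will be added as potential covariates for the statistical models described in Hypothesis 1a". The result expected under the hypothesis is "we would expect to observe an inverse relationship (negative coefficient) between initial bone mass, physical activity, grip strength, and change in BMC", and the sentence goes on to qualify that change by group or by unit of strain. No interaction term is named.

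The SAP does not name a separate scan as the source of initial BMC. It gives no BMC precision or reliability and does not mention regression to the mean.

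**The concern.** The natural reading is that initial BMC is the baseline value of the outcome variable itself. An error in that scan then enters the predictor with a plus sign and the change score with a minus sign. A woman whose baseline is read too high appears both to start with more bone and to gain less. This gives a negative slope even when initial bone mass has no bearing on adaptation, and a negative slope is what the SAP expects to see if 1b is right.

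At stake is the initial-bone-mass part of 1b, in both experiments, since the SAP applies the same plan to each. Grip strength and physical activity are not subtracted to form the change, so their coefficients do not carry this error.

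**Working it through.** The plan gives no sample-size, alpha or precision figure for 1b, so there is no figure of its own to reproduce.

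**Expected slope.** Let observed baseline be B = T + e0 and follow-up be T + D + e1, where T is true baseline, D is true change, and e0 and e1 are scan errors. Then change C = D + e1 − e0. If D is independent of T, the slope of C on B is

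−var(e0) / [var(T) + var(e0)].

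For a between-woman SD of 10% of mean BMC:
- 1% error: −1/(100 + 1) = −0.010
- 2% error: −4/(100 + 4) = −0.038
- 3% error: −9/(100 + 9) = −0.083

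For an SD of 15% and 1% error: −1/(225 + 1) = −0.004.

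**False support.** From the Protocol, Group Assignment: 20 low, 20 high and 20 control, so 60 women per experiment. Assumed, because the documents do not give them: between-woman SD 10% or 15%, the error SDs below, SD of true change 1% or 2% in loaded women, and no true association in absolute change. The pilot figures +0.51% and +2.57% (Protocol, Rationale for Doses) served as the low and high group means. The table shows the simulated share of trials with a coefficient significantly below zero at two-sided 5% (nominal 2.5%). The four-visit model was run on each woman's mean change, with true change held constant over visits.

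| Error SD | 12-month, SD 10% | 12-month, SD 15% | Four-visit, SD 10% | Four-visit, SD 15% |
|---|---|---|---|---|
| 1% | 5–6% | 4–5% | 5–7% | 5–6% |
| 2% | 15–17% | 10% | 18–25% | 12–14% |
| 3% | 31–32% | 16–18% | 43–49% | 22–27% |

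At 0.7% error, the 12-month model gives 3–5%. Averaging four visits does not dilute the baseline error, because all four change scores share it.

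**Which row is plausible.** Rationale for Doses reports eight pilot women classified by observed 14-week ultradistal BMC change: five at +2.57% and three at +0.51%.
- Gap: 2.57 − 0.51 = 2.06 points.
- If these are subgroup means after sorting on observed change, the expected gap between the top five and bottom three of eight normal values is 1.47 SD.
- Implied SD of observed change: 2.06/1.47 = 1.40%.
- If all of this were error from two scans: 1.40/√2 = 0.99% per scan.
- If true change had an SD of 1%: √[(1.40² − 1)/2] = 0.7% per scan.
- With a true-change SD of 0–1%, a gap of 2.06 or less has a chance of about 2–3% at 2% error and 0.2% at 3% error.

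**Dependence on units.** The SAP does not say whether change is absolute or percent. If it is absolute and all women in a group gain the same percentage, larger bones gain more. With the pilot means, the added slope is (0 + 0.51 + 2.57)/3 = 1.03%, or +0.010. At 1% error and SD 10% the net slope is −0.010 + 0.010 = 0, and simulated false support is 2.3%. At SD 15% the net is −0.004 + 0.010 = +0.006, with 1.0%. At 2% error and SD 10% the net is still negative: −0.038 + 0.010 = −0.028. With a percent-change outcome this offset disappears.

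**Remedies under the same null.** Taking initial BMC from a measurement with independent error gives a mean slope of about 0 and false support of 2.2–3.0%. Testing the initial BMC × strain interaction with controls included gives a mean coefficient of about 0 and 1.0–3.0%.

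**The case against.** Four arguments reduce the point, and most of each stands.

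- **Size.** The only precision evidence in the documents is the pilot, and it points to about 1% error or less. A reader might infer from the lower rows of the table that scanner noise would often confirm 1b. The documents do not support that. The pilot is limited (eight women, ultradistal rather than whole-radius BMC, scanner not named), so it makes errors of 2% or more unlikely without excluding them.
- **Direction.** A reader might infer that the bias always favours the sponsor's prediction. That is true only of the noise term. Proportional gains measured in absolute units push the other way and can cancel it at about 1% error.
- **Interaction.** The wording about a given strain magnitude, and about change by group or per unit strain, can be read as effect modification. A baseline-by-strain interaction would cancel the shared error because it is common to all groups. But the SAP specifies only added covariates. Slopes fitted in loaded women alone, or within one group, would keep the artefact: at SD 10% and 2% error, false support is 11.2% and 7.5% respectively.
- **Decision rule.** The SAP describes what it would expect to observe, for three covariates together, and sets no alpha for 1b. It is an interpretive prediction, not a formal rejection rule. It still treats the sign as support.

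It would also be wrong to infer that baseline adjustment harms Hypothesis 1a. A baseline covariate does not bias the randomised group contrasts; the difficulty lies only in reading its own coefficient as biology.

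**Conclusion.** The point holds for the initial-bone-mass part of Hypothesis 1b, provided that initial BMC is the same baseline scan that is subtracted. The main-effect test is then not centred on zero, and nothing elsewhere in the SAP corrects for it. At the precision the pilot suggests, false support is about 3–7% against a nominal 2.5%. It becomes material only at about 2% error and above. These rates rest on assumed between-woman SDs of 10–15% and no true association in absolute change; proportional gains in absolute units would reduce or remove the excess at about 1% error. Severity is minor to moderate: one covariate of a subsidiary hypothesis is affected, and the primary group comparisons are not.

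**What to change.** In Hypothesis 1b, state that a negative main-effect coefficient on the same-scan baseline BMC is not evidence for the hypothesis, and say whether the change score is absolute or percent. Then test initial bone mass in one of two ways.

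(a) Use a baseline measurement that does not enter the change score. First name the scanner that supplies whole-radius BMC, which the documents do not do. Then take initial bone mass from another planned baseline scan of that radius, or from the opposite radius. The Protocol's Radiation Dose section already counts CT on both arms ("1 DXA plus 1 CT scan per arm x 2 arm x 9 mrem/scan") as well as HR-pQCT on each arm. Confirm that the chosen scan falls at baseline and covers a comparable region.

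(b) Test the initial BMC × strain (or × group) interaction with controls included. This cancels the shared error and matches the hypothesis as worded.

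Same-scan baseline BMC may stay in the Hypothesis 1a models as a precision covariate whose coefficient is not interpreted.

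The cost is SAP wording and a changed model term; no new scan is needed if a planned one serves. Option (a) mildly attenuates the coefficient because the second measure is a proxy. Option (b) has less power than a main-effect test.
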